3.2 Primary and secondary endpoints

Primary endpoint:

Fold-change in the intensities of features determined by mass spectrometry according to genotype (PMs versus NMs-RMs-UMs) and according to sessions. Metabolic features showing a fold-change ≥ 1.5 or ≤ 0.67 ³⁷ will be qualified as CYP2C19 endogenous biomarkers. Chromatographic signals will be detected in healthy volunteers' urine, plasma and liver-derived

extracellular vesicles by liquid chromatography coupled to high resolution mass spectrometry (LC-HRMS) at each session for each volunteer.

Secondary endpoint:

- Correlation of significant ions measured in metabolomics with OH-OPZ/OPZ blood ratio.
- Establishment of a multivariate linear regression model to predict CYP2C19 phenotype.

3.3 Potential risks and benefits for the volunteers

There will be no personal benefits for the volunteers included in this study besides the possibility to know their CYP genotype and phenotype if they are willing to. Potential risks include the occurrence of adverse events related to fluvoxamine (described in detail in section 5.1.2), rifampicin (described in detail in section 5.1.3), venous and capillary blood sampling (minimal risk category: local pain, infection, haematoma) and the rare occurrence of omeprazole adverse events (described in detail in section 5.1.1).

3.4 Study duration for subjects and stopping rules

Apart from the screening session (visit 1), the minimal study duration will be 24 days (day 0-27±4d) including 3 half-days spent in the HUG (visit 2, 3 and 4).

Volunteers will be able to withdraw from the study at any time without any explanation or justification. The data collected up at this moment will be conserved and used unless the volunteer wants its signed informed consent withdrawn. The investigator will also have the possibility to exclude a volunteer from the study for safety reasons or lack of compliance.

3.5 Data collected in the eCRF

All data described in section 7.1.1. will be reported in the eCRF. A list of all participants will be kept, with the date of inclusion and the date and reason for drop-out if applicable.

4. STUDY POPULATION

4.1 Selection and recruitment procedures

Volunteers will be recruited through advertisements approved by the “commission cantonale d’éthique et de la recherche” (CCER) of Geneva and displayed in different public buildings or

transmitted by email and social media. After a first contact (either telephonic or by e-mail), potential volunteers will be invited to participate to an information session at which the study aim and design as well as possible risks will be explained. After allowing at least 72 hours for reflection, volunteers willing to participate in the study will sign the consent form. In the next step, they will be subject to a screening procedure including a review of volunteer's medical history and current health status, physical examination, hepatic and renal tests, body mass index determination, pregnancy test (for women) and genetic testing for CYP2C19.

After evaluation of the inclusion and non-inclusion criteria, eligible volunteers will be allocated to a study group (CYP2C19 PMs or NMs-RMs-UMs) and will attend sessions 1, 2 and 3.

4.2 Inclusion criteria

- Healthy men and women
- Age 18-65 years
- Body Mass Index (BMI) 18-27
- Understanding of French language and able to give a written informed consent
- CYP2C19 genotype: PMs, NMs, RMs or UMs
- At least one barrier method contraception during the whole study and 1 month after the end of the study (in addition of hormonal contraception if applicable)

4.3 Non-inclusion criteria

- CYP2C19 IMs
- Participation in any other interventional clinical study within 3 months prior to inclusion
- Pregnant or breastfeeding woman
- Any pathologies, use of drugs or food that may affect CYP activity (based on the 'drug interactions and cytochromes P450 table published by the Service of Clinical Pharmacology and Toxicology, HUG⁵⁰ and on the investigator's knowledge)
- Medical history of liver transplantation
- Regular smokers of ≥ 10 cigarettes/day
- Alcohol intake 2 days prior to session 1 and during fluvoxamine and rifampicin intake
- Alteration of hepatic tests (ASAT, ALAT, GGT, bilirubin more than 3x normal)
- Renal failure (serum urea, serum creatinine and eGFR outside the norms)
- Medical history of chronic alcoholism or abuse of psychoactive drugs
- Sensitivity to any of the drugs used

- Psychiatric disorders
- Beck Score ≥ 10 (question related to suicide >0)
- Contact lens wearers

4.4 Assignment to study groups

Each eligible participant will be assigned to a study group according to his CYP2C19 genotype. The first group will be composed of carriers of two non-functional alleles of CYP2C19 (PMs). The second group will be composed of carriers of two normally functional alleles (NMs), one normally functional allele and one increased-functional allele (RMs) or two increased-functional alleles of CYP2C19 (UMs).

IM subjects will not be included in the clinical study because of the intermediate activity of the enzyme that may not highlight significant changes in the metabolome when compared to the metabolome of PMs or NMs. In addition, NMs, RMs and UMs are grouped together because of the potentially low changes in the metabolome between them as it has been found for the endogenous DHETs blood levels and many exogenous compounds such as omeprazole, pantoprazole and lansoprazole.^{8,10,11,40,51}

4.5 Withdrawal criteria

Volunteers are free to withdraw from the study at any time without giving any explanation. If a volunteer withdraws from the study, a new volunteer will be included. The investigators may exclude a volunteer from the study for medical reasons or when eligibility criteria are not fulfilled anymore.

5. STUDY INTERVENTION

5.1 Identity of Investigational Products

5.1.1 Omeprazole

Omeprazole is the exogenous administrated probe used for CYP2C19 phenotyping. A unique intake of this drug at 10 mg will be performed at each session, for a total of 3 sessions.

Omeprazole is specifically metabolised to an inactive metabolite, OH-omeprazole (OH-OPZ), by CYP2C19.^{52,53} It is a first-generation proton pump inhibitor used to treat gastroesophageal reflux disease, gastric and duodenal ulcers and other gastric disorders. Its mechanism of action consists of reducing gastric acidity by inhibiting the secretion of gastric acid. The level of individual omeprazole exposure varies depending on several factors such as the dose and

the drug PK features like absorption rate and metabolism kinetics, as well as individual characteristics like age or CYP2C19 genotype.⁵⁴ The usual posology of omeprazole is 20 mg once a day for 2 weeks. This dose is commonly increased to 40 mg and the treatment duration can be expended to 4 weeks if necessary. A dose of 10 mg, corresponding to the prophylactic dose, will be administered in this study.⁴⁵

Omeprazole is rapidly absorbed after oral administration, with an absolute bioavailability of 30-40% at doses of 20-40 mg. The maximal plasmatic concentrations are achieved 0,5-3,5 hours after the administration. The elimination half-life of omeprazole is 0,5-1 hour in healthy CYP2C19 NMs, but can be up to three times longer in healthy CYP2C19 PMs.^{46,53}

Adverse effects with standard doses of omeprazole (20-40 mg) are generally rare but headaches, nausea, diarrhoea and/or other gastro-intestinal disturbances may occur.⁴⁵ During this clinical trial, adverse effects of omeprazole are highly unlikely.

DBS sampling method using 10 µl of capillary blood obtained from a small finger prick will be performed 2 hours after omeprazole intakes. This sampling procedure has the advantage to be less invasive, more cost-effective and easier to transport and store in comparison to the standard venous blood sampling.⁵⁵

5.1.2 Fluvoxamine: CYP2C19 inhibitor

Fluvoxamine is an antidepressant drug of the selective serotonin reuptake inhibitor (SSRI) class. It is used as a medical treatment in depression, as well as in anxiety disorders. The usual starting dose of fluvoxamine is 50 mg per day. The daily dose can be increased to 100 mg once a day and up to a maximum of 300 mg per day taken in divided doses (e.g. 150 mg twice a day) for non-responding patients.⁴⁷ In this study, the dose administered is 50 mg once a day for 7 days.

Following oral administration, fluvoxamine is rapidly and almost completely absorbed in the gastrointestinal tract. However, it is also subject to hepatic first-pass metabolism, resulting in an absolute bioavailability of 53%. Steady-state maximal concentrations are reached between 10 to 14 days.⁴⁷⁻⁴⁹ Fluvoxamine is extensively metabolized in the liver by CYP2D6 and CYP1A2 to at least 11 different metabolites, of which no one is known to be pharmacologically active.⁵⁶⁻⁵⁹ These metabolites are widely eliminated in urine, with a variable fluvoxamine elimination half-life of about 19,5 hours (range 17-22 hours) after multiple intakes.⁴⁷⁻⁴⁹ Adverse effects of fluvoxamine are those of SSRIs, which include asthenia, tremor, somnolence, insomnia, gastro-intestinal disorders and erectile dysfunction. In patients suffering from depression, a deterioration of the depressive symptoms and/or suicidal ideation or behaviours may appear with fluvoxamine intake.⁴⁷ Consequently, subjects with any psychiatric disorders

will be excluded. Moreover, to ensure the recruitment of psychically healthy subjects, risk of depression and/or suicidal ideation will be assessed with the Beck Depression Inventory (see Section 4.6). Antidepressant discontinuation syndrome (ADS) has been described in case of abrupt cessation generating the following symptoms: dizziness, sensorial troubles, sleep disorders, agitation, anxiety, nausea, tremor, sweating, headaches, and emotional instability. In most patients, the intensity of these symptoms was minor and disappeared spontaneously.⁴⁷ Moreover, ADS is unlikely when treatments are taken less than 5-8 weeks.^{60,61} In this study, a total of 7 doses of fluvoxamine 50 mg spread over 7 days will be given to volunteers, which minimizes the risk of experiencing adverse events and ADS. Fluvoxamine acts as a potent inhibitor of CYP2C19 and CYP1A2, and a moderate inhibitor of CYP2C9, CYP2D6 and CYP3A4.^{15,16,47,62,63} It is mainly metabolized to fluvoxamine acid through CYP2D6, representing its major metabolic pathway, along with minor contributions of CYP1A2.^{50,56-59,63} In this clinical trial, we will administer fluvoxamine for 7 days to be able to observe a decrease in the concentration of endogenous CYP2C19 metabolites with a relatively long half-life. It is not relevant to detect metabolites with a longer half-life as it may not allow the detection of rapid changes in the phenotype. Moreover, the steady-state of fluvoxamine should be almost reached after 7 days of dosing at 50 mg.^{48,49}

5.1.3 Rifampicin: CYP2C19 inducer

Rifampicin is rifamycin antibiotic used to treat infections such as tuberculosis, leprosy, meningitis, and staphylococcal infections. The usual dose of rifampicin depends on the type and severity of the infection being treated, as well as the patient's age, weight, and other medical conditions. The standard adult dose ranges from 600 to 1200 mg per day.⁶⁴⁻⁶⁶ In this study, the dose administered is 600 mg (i.e. 2 tablets of 300 mg) once a day in the evening for 10 days.

Following oral administration, rifampicin is rapidly and almost completely absorbed. Food intake can reduce the absorption of rifampicin. Consequently, it is usually taken 1 hour before or 2 hours after a meal. Steady-state maximal concentrations are reached within 7 days.⁶⁴⁻⁶⁷ Rifampicin is extensively metabolized in the liver to the active compound 25-O-desacetylrifampicin, which is further metabolized into inactive compounds.^{64-66,68} These metabolites are primarily excreted in the bile (80%), with a small amount eliminated in the urine (4-18%). Rifampicin elimination half-life is dose-dependent and is approximately 1 to 2 hours after multiple doses of 600 mg per day.^{64,69} Common adverse effects of rifampicin include gastrointestinal disturbances like nausea, vomiting and diarrhoea as well as flu-like symptoms such as fever, chills and headache. These adverse effects are generally mild and resolve once

the medication is discontinued. In addition, rifampicin is responsible of staining contact lens (in addition of urine, sweat, sputum and tears), from which contact lens wearers are excluded from the study. Because Rifampicin is contraindicated in case of severe renal impairment, renal tests (i.e. serum urea, serum creatinine and eGFR) were included during the initial screening procedure of this study in order to exclude all renal impairment cases.

Rifampicin acts as a strong inducer of CYP2C8, 2C9, 2C19 as well as 3A4/5 and a weak inducer of CYP1A2 and 2B6.^{17,24,50,64,70,71} Consequently, many concomitantly administered classes of drugs such as benzodiazepines, calcium antagonists, protease inhibitors and neuroleptics become ineffective. This also includes oral contraceptives, which makes barrier contraceptive method an important requirement. Furthermore, induction does not dissipate until 2 weeks after discontinuing rifampicin, reinforcing the need to use a barrier contraceptive method after stopping treatment (i.e. male or female condom, spermicide or diaphragm).^{64,70,72} In this study, at least one barrier contraceptive method will have to be used for all the study duration and for 1 month after the last visit (session 3). During this period, women who usually take oral contraceptives can keep their intake while using a barrier contraceptive method. It is necessary to administer rifampicin for at least 7 days to achieve the onset of full enzymatic induction. Therefore, 10 days will be applied here, which is sufficient to increase the concentration of endogenous CYP2C19 metabolites.⁷²

5.2 Packaging, Labelling and Supply

The medications for this study will be purchased from the HUG Pharmacy. They will remain in their original primary packaging (blister packs). A pharmacist from the Division of Clinical Pharmacology and Toxicology will handle the labelling and distribution. Each drug package will be labelled with the product name, dosage form, strength, batch number, expiry date, patient number, and the warning “tenir hors de portée des enfants.” Additionally, the labels will include the protocol number and name, the statement “use only as part of a clinical trial,” and the name of sponsor and principal investigator. For fluvoxamine and rifampicin, healthy subjects will receive the exact number of tablets required for home use (7 tablets for fluvoxamine and 20 tablets for rifampicin) in a labelled ziplock bag.

5.3 Storage conditions

The storage of the drugs used in this study will be ensured by a pharmacist of the Division of Clinical Pharmacology and Toxicology. Drug packages used in this study will be labelled with the mention “store at room temperature”.

5.4 Compliance with study intervention

Fluvoxamine and rifampicin intakes will be monitored by taking back empty blisters at session 2 and 3 respectively. Fluvoxamine and rifampicin plasma concentrations will also be quantified using a validated LC-MS/MS method.

5.5 Data Collection and Follow-up for withdrawn participants

In the event of withdrawal from the study, the data collected up to this moment will still be conserved and analysed. In such a case and if needed, the investigator will provide all necessary information and medical care (including adequate medical referrals) to the volunteer.

5.6 Trial specific preventive measure

Healthy subjects will be asked to inform the investigator or another collaborator of the study of all concomitant medication they might take during the study.

Women will be asked to use at least one barrier contraceptive method (i.e. male or female condom, spermicide or diaphragm) throughout all the study duration and for 1 month after the last visit (session 3). Pregnancy test will also be performed during each session to ensure absence of pregnancy.

Participants will be asked to stop driving and using dangerous machinery while fluvoxamine is administrated.

During the inclusion session, the Beck Depression Inventory will be used to exclude any potential symptoms of depression as well as suicidal ideation and behaviours. It is a 21-question multiple choice self-rated scale. The maximum score is 63 and indicates severe depression. Total score of 0-9 represents minimal range.⁷³ Therefore, subjects with score ≥ 10 will be excluded from the study. Furthermore, only a score of 0 for the question related to suicide will be accepted.

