3. STUDY DESIGN

3.1 Overall description

The study will be an open-label study with a total of 40 healthy volunteers fulfilling inclusion/non-inclusion criteria, divided into 2 study groups: 10 healthy volunteers PMs and 30 NMs-RMs-UMs for CYP2C19 and participating in the three sessions:

- Session 1: urine and venous blood sampling. Determination of blood $MR_{OH-OPZ/OPZ}$ at baseline (no inhibitor administrated).
- Session 2: urine and venous blood sampling. Determination of blood $MR_{OH-OPZ/OPZ}$ after pre-treatment by fluvoxamine (strong inhibitor of CYP2C19).

- Session 3: urine and venous blood sampling. Determination of blood MR_{OH-OPZ/OPZ} after pre-treatment by rifampicin (strong inducer of CYP2C19).

Information:

At this step, the volunteer will have an interview with one of the co-investigators at the Clinical Pharmacology and Toxicology department and the study will be explained in detail. A sufficient time will be allowed before the inclusion session to guarantee sufficient time for reflection.

Inclusion:

Volunteers willing to participate and having signed the informed consent form (ICF) will undergo a clinical evaluation with a physician including liver and kidney tests, body mass index, genotyping (except if CYP2C19 genotype is already known) and a pregnancy test (women only). Women will be asked to use at least one physical contraceptive barrier (i.e. male or female condom, diaphragm, spermicide) throughout their study participation and 1 month after the end of the study, in addition of their hormonal contraception if applicable. In case of heavy menstrual bleeding, women will have to be recruited before or after their menstrual period to avoid the presence of blood in urine. In addition, all volunteers will be asked to avoid alcohol consumption on days of taking study drugs and 48 hours before day 0 of session 1. A volunteer code for the study will be assigned to each volunteer included in the study.

Only volunteers fulfilling the inclusion/non-inclusion criteria will be allocated to a study group.

Sessions course:

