Each session includes urine collection over a full 24-hour period that will start in the morning of day 0 for session 1, day 10±4d for session 2 and day 26±4d for session 3. It will end in the morning of day 1 for session 1, day 11±4d for session 2 and day 27±4d for session 3. Since most of this part will be performed at home, subjects will be given precise instructions on how to perform it. The last urine stream for each session will be collected in the morning after an overnight fast. Urine will be collected into a 24-hour collection container. This will be stored in a cooler with ice packs and/or a refrigerator.

Immediately after the 24-hour urine collection, venous blood (6 x 6 ml) will be collected and one 10 mg tablet of omeprazole (Antrumups®) administrated. Women will only receive omeprazole after verifying that they are not pregnant (urine test). 2 hours after omeprazole intake, capillary blood sampling (DBS sampling) will be performed. Volunteers will then be free to leave the HUG. Breakfast will be served after capillary blood sampling.

No wash-out period is necessary between the first and second session as fluvoxamine treatment lasts one week, which is sufficient to eliminate omeprazole administered in the first session, as well as its metabolites. Indeed, omeprazole's half-life elimination is generally less than 1 hour, and does not exceed 3 hours in PMs healthy subjects^{45,46}. However, a minimum of six days is necessary between session 2 and session 3. This time gap is required because of the half-life elimination of fluvoxamine being 19,5 hours on average after multiple intakes⁴⁷⁻⁴⁹.

Concerning the second session, participants will be instructed (orally and through reception of an instruction card) to take one 50 mg tablet of fluvoxamine (Floxyfral® junior) every morning for one week (7 doses in total) with the breakfast. If the third visit (session 2) happens exactly 7 days after the second visit (session 1), the drug must be taken during the lunch of session 1 (day 1) in order to have a total of 7 doses of fluvoxamine administrated. Otherwise, the treatment must start one week before the third visit (session 2) and the last dose must be taken 2 hours before omeprazole intake during the day 1 of session 2.

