7.2 Adverse events collection and grading

Drugs used in this study are approved in Switzerland and their security profile is well known. Therefore, AEs of grade ≥ 2 , SAEs and SUSARs are unlikely. If that were to happen, only SAEs that result in death and SUSARs would be reported in the eCRF.

AE monitoring and filling out of the eCRF for each participant begins when they receive omeprazole during the second visit (session 1). This monitoring will continue throughout the two-hour duration of the visit and the same procedure will be followed for the third visit (session 2) and the fourth visit (session 3). To ensure comprehensive safety monitoring, a follow-up phone call will be conducted two days after each visit, including the fourth one (final safety follow-up). This allows for the early detection of any potential AEs related to fluvoxamine and rifampicin, as well as adverse events that may appear after the study. Participants will be encouraged to contact study investigators at any time if they experience an AE, even if it occurs after the study has ended. This is particularly important if the participant feels they need to discontinue the medication during the study or if they require medical assistance.

The eCRF report will document the reasons for notification (e.g. death, life-threatening event), the date of first occurrence, and a description of SAEs/SUSARs. The report will also assess the nature of the SAE (expected or unexpected) and its relationship to the study drug (imputability) to determine if it qualifies as a SUSAR. Additionally, information on any potentially responsible medications will be recorded.

All AEs, SAEs and/or SUSARs will be followed up until the event is resolved. The SAEs that are not reported in the eCRF and AEs of grade ≥ 2 will be recorded in the electronic medical records of HUG for each study subject by the investigator.

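### The driving and machinery precaution ends with fluvoxamine dosing and does not cover the day after the last tablet

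*Protocol*

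**What the plan says.** Section 5.6 holds the only driving rule in the protocol: "Participants will be asked to stop driving and using dangerous machinery while fluvoxamine is administrated". It gives no period after the last tablet. The same section does carry another precaution past dosing: barrier contraception continues for one month after the last visit.

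The timing of the last tablet is in section 3.1: "the last dose must be taken 2 hours before omeprazole intake during the day 1 of session 2". The capillary sample follows 2 h after omeprazole, and then "Volunteers will then be free to leave the HUG". Discharge is therefore about 4 h after the last tablet.

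Section 5.1.2 gives a "variable fluvoxamine elimination half-life of about 19,5 hours (range 17-22 hours) after multiple intakes", states that "a total of 7 doses of fluvoxamine 50 mg spread over 7 days will be given to volunteers", and lists the adverse effects of the class, "which include asthenia, tremor, somnolence, insomnia, gastro-intestinal disorders and erectile dysfunction". Section 7.2 adds that "a follow-up phone call will be conducted two days after each visit".

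**The concern.** A rule tied to administration stops when tablets stop, but the drug does not. At a half-life close to 20 h and after a week of daily dosing, an appreciable amount is still present the next day. The protocol names somnolence, tremor and asthenia as fluvoxamine effects, and these are plausible reasons for a driving bar. A volunteer who follows section 5.6 as written may drive or use machinery the day after session 2.

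The two-day call comes after that day, so it can pick up a problem but cannot prevent next-day driving. The participants are healthy volunteers with no personal benefit beyond learning their genotype and phenotype (section 3.3), and third parties are also exposed. Only safety wording is at stake. Sample size, endpoints and analysis are unaffected.

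**Working it through.** The protocol states no post-dose driving period, so there is no figure of its own to reproduce. The check asks how the level on the day after the last tablet compares with levels at which the bar applies.

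**Inputs from the protocol.** Half-life h = 19.5 h, range 17-22 h (section 5.1.2); 7 doses of 50 mg (section 5.1.2); one dose each morning, so a 24 h interval (section 3.1).

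**Assumptions.** One compartment, linear kinetics, the multiple-dose half-life applied from the first dose, and absorption time ignored in the base case. Levels are expressed relative to the peak after a single 50 mg dose.

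**Formulas.**
- Fraction left after one interval: r = 2^(-24/h). This is also the level 24 h after the first tablet.
- Peak after the seventh dose: A = (1 - r^7)/(1 - r).
- Level 24 h after the last tablet: A × r. Level 48 h after: A × r².
- Time after the first tablet with the same level as 24 h after the last: -h × log2(A × r).

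**Results.**

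| Half-life | r | A | 24 h after last tablet | 48 h after last tablet | Matching time after first tablet |
|---|---|---|---|---|---|
| 17 h | 0.376 | 1.60 | 0.60 | 0.23 | 12.5 h |
| 19.5 h | 0.426 | 1.74 | 0.74 | 0.32 | 8.4 h |
| 22 h | 0.469 | 1.88 | 0.88 | 0.41 | 4.0 h |

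On the first dosing day the level runs from 1 down to r, that is to 0.43 (0.38-0.47). In every row the level 24 h after the last tablet lies between r and 1. It is therefore within the range seen on a day when driving is barred. By 48 h the level is below r in every row.

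**Sensitivity.** A first dose at lunch (first gap about 19 h, assumed) leaves the 24 h value at 0.74 for h = 19.5 h. The protocol gives no absorption rate. With an assumed first-order rate of 0.3-2 per h, the 24 h level becomes 0.67-1.28 of a single-dose peak across the half-life range, so ignoring absorption does not overstate the gap.

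**Size of a 48 h margin.** 48/22 = 2.2 and 48/17 = 2.8, so 48 h is about 2-3 half-lives.

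**The case against.** **The rule is not wrong, only short.** Nothing in section 5.6 contradicts another section. That is correct, and the point is offered as an improvement. It is more than missing detail, because the rule does fix an end and that end comes early.

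**Other documents may say more.** Volunteers receive oral instructions and an instruction card (section 3.1) and an information sheet (section 10.6). Their text is not available here and may address when to resume driving. This limits confidence, but the protocol rule would still need to match.

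**The rule might be read as lapsing at discharge.** A reader might infer that a volunteer leaving about 4 h after the last tablet is already free to drive, at a level above a single-dose peak. The documents do not support this. With once-daily dosing, such a reading would also lift the bar between tablets on every day of the course. The natural sense is the treatment course, including the day of the last tablet. The neighbouring alcohol rule, under which volunteers are "asked to avoid alcohol consumption on days of taking study drugs", is worded by day.

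**Equal level is not equal risk.** The bar follows the course of treatment and uses no concentration threshold. Nothing in the protocol shows that a given level carries the same risk on day 1 as after a week. Relative to the volunteer's own last-dose peak, the level is r = 43% at 24 h and r² = 18% at 48 h (h = 19.5 h). This objection stands: the comparison shows persistence and does not show impairment.

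**The model is crude.** At h = 19.5 h it reaches 1 - r^4 = 97% of steady state by dose 4 and over 99% by dose 7. Section 5.1.2 speaks of 10 to 14 days, and of steady state being almost reached at day 7. The second decimals should carry no weight. A slower approach to steady state gives no reason to expect a lower next-day level, so the direction is unlikely to reverse.

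**Exposure is modest.** The dose is the usual starting dose, given for seven days to screened volunteers who may contact the investigators at any time. This keeps the point minor.

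**Conclusion.** The point holds as a minor safety gap. Section 5.6 covers driving and machinery through the day of the last fluvoxamine tablet but not the next day. The level is then roughly 0.6-0.9 of a single-dose peak, within the range of the first dosing day. This rests on linear one-compartment kinetics, the protocol's 17-22 h half-life and seven doses 24 h apart.

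Two further inferences should be resisted. First, residual drug is not evidence that volunteers would be impaired, and the protocol sets no level at which driving becomes safe. Second, the minimum six-day interval before rifampicin (section 3.1) might be taken as an admission that the driving bar should last as long. That interval serves the separation of the fluvoxamine and rifampicin sessions and says nothing about driving. Confidence is medium, because the instruction card and consent text are not available.

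**What to change.** Amend section 5.6 so that the bar on driving and dangerous machinery applies while fluvoxamine is administered and for 48 hours after the last dose. Repeat this on the instruction card and at session 2 discharge. Use the existing call two days after session 2 to ask about somnolence or tremor before driving resumes.

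The 48 h is a pragmatic margin: about 2-3 half-lives, a level of about 0.2-0.4 of a single-dose peak, and the timing of a call that is already planned. It is not a derived threshold, and a longer period could be argued from the same inputs (the model gives about 0.1-0.2 at 72 h).

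The cost is one sentence in the protocol, one line on the card and one question in the call. No visit or call moves. Each volunteer goes about one extra day without driving or using machinery.
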